## **Study Protocol**

This project aims to evaluate safety and security of patients submitted to minimally invasive radical prostatectomy, who received discharge from hospital in the same day of the surgery (Group I), on the 1st post-surgery day (Group II) and in the 2nd post-surgery day (Group III – control). The specific aims are the evaluation of fail index and factors that influence the permanence in the hospital, the satisfaction of patients, the perception of security of patient, the index of post-discharge complications and the costs related to different times of hospitalization. On randomization, those patients in Group I must match the early hospital discharge criteria defined in the study. Thus, they will be forwarded to "Casa de Apoio Madre Paulina", where will receive nursing care until the next day when, in the morning, will be reevaluated in the ambulatory of urology from Barretos Cancer Hospital. The patients of Group II will be evaluated in the ambulatory in the 2nd postsurgery day, before the discharge. In the Group III (control), the patients will be discharged in the 2nd post-surgery day (routine of Barretos Cancer Hospital). All patients who accept to be enrolled in the study will sign the Consent Term previously the surgery. At the 10th post-surgery day, in the follow-up, it will be applied the questionnaire SATISBR and an inventory.

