## Statistical Analysis Plan

This project aims to evaluate safety and security of patients submitted to minimally invasive radical prostatectomy, who received discharge from hospital in the same day of the surgery (Group I), on the 1st post-surgery day (Group II) and in the 2nd post-surgery day (Group III – control). The specific aims are the evaluation of fail index and factors that influence the permanence in the hospital, the satisfaction of patients, the perception of security of patient, the index of post-discharge complications and the costs related to different times of hospitalization. On randomization, those patients in Group I must match the early hospital discharge criteria defined in the study. Thus, they will be forwarded to "Casa de Apoio Madre Paulina", where will receive nursing care until the next day when, in the morning, will be reevaluated in the ambulatory of urology from Barretos Cancer Hospital. The patients of Group II will be evaluated in the ambulatory in the 2nd postsurgery day,

before the discharge. In the Group III (control), the patients will be discharged in the 2nd post-surgery day (routine of Barretos Cancer Hospital). All patients who accept to be enrolled in the study will sign the Consent Term previously the surgery. At the 10th post-surgery day, in the follow-up, it will be applied the questionnaire SATISBR and an inventory. The data will be descriptive considering average, standard deviation, minimum and maximum value and quartile to the quantitative variables and frequency tables to the qualitative variables. In order to determine the groups' homogeneity, some sociodemographic and clinical characteristics will be compared. To the qualitative variables, it will be used chi-squared test (of Fishers exact test), and to the quantitative variables it will be used variance analysis (or Kruskal-Wallis test). The patients' satisfaction will be measured using SATIS-BR, which consists in three numeric domains (ranging from 1 to 5). The comparison of each domain among the groups will be performed using ANOVA. Then, linear regression will be performed in order to analyze the relationship of the patients' characteristics influencing the satisfaction. The rates of fail, clinical security, security perception and post-discharge complications will be compared among the groups using chi-squared test (of Fisher's exact test). There will be considered the significance level of 5%.

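### The four rates get a three-group test and frequency tables, but no difference with precision against the control group and no common window for complications

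*Combined protocol and SAP*

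**What the plan says.** The Study Protocol section opens: "This project aims to evaluate safety and security of patients submitted to minimally invasive radical prostatectomy". The patients are those "who received discharge from hospital in the same day of the surgery (Group I), on the 1st post-surgery day (Group II"), and a third group discharged on day 2. The Statistical Analysis Plan section repeats this and calls the third group the control: "In the Group III (control), the patients will be discharged in the 2nd post-surgery day", which it describes as the hospital's routine.

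For the categorical results the SAP plans two things. One is description, with "frequency tables to the qualitative variables". The other is a test: "The rates of fail, clinical security, security perception and post-discharge complications will be compared among the groups using chi-squared test" (or Fisher's exact test). The level is given once for everything: "There will be considered the significance level of 5" per cent.

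The only regression is linear and concerns satisfaction. Neither section names a pairwise or post-hoc comparison, a risk difference or ratio, a confidence interval, a margin or a multiplicity rule.

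On timing, the one follow-up contact described for all groups is this: "At the 10th post-surgery day, in the follow-up, it will be applied the questionnaire SATISBR and an inventory". No start or end of the period for counting complications is stated.

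**The concern.** The plan names a control but specifies no comparison with it. A chi-squared test on three groups asks whether the three rates are all equal. A reader deciding about early discharge needs something else: by how much the complication rate could be higher than under routine care, given the data. The planned test does not report that limit.

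The post-discharge endpoint adds a second difficulty to any contrast with control. By design, discharge is on the day of surgery in Group I and on day 2 in Group III. A complication on day 1 is post-discharge in Group I and an in-hospital event in Group III. The count then favours later discharge even if the complications are the same.

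At stake is whether the trial can report a usable safety comparison, not whether the planned test is valid. It is valid.

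**Working it through.** **Inputs from the documents.** Three groups, Group III as control, a chi-squared or Fisher test and a 5% level. No sample size, expected rate or margin is given, so there is no figure of the plan's own to reproduce.

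**Assumptions, for illustration only.** A yes/no outcome, equal groups of 50, 100 or 150, and 10% observed in Groups II and III. Intervals are Newcombe at 97.5% (z = 2.241), which is Bonferroni for two contrasts. Counts are in the order I/II/III.

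**1. A non-significant test at 100 per group, counts 20/10/10.**
- Expected events per group: 40/3 = 13.33; expected non-events: 86.67.
- Sum of squared deviations: 6.67² + 3.33² + 3.33² = 66.67.
- Chi-squared = 66.67 × (1/13.33 + 1/86.67) = 5.77. On 2 df, p = exp(-5.77/2) = 0.056.
- Wilson 97.5% limits: 20/100 gives 12.57% to 30.30%; 10/100 gives 5.08% to 18.75%.
- Group I minus III = +10 points.
- Upper limit: 10 + √[(30.30 - 20)² + (10 - 5.08)²] = +21.4.
- Lower limit: 10 - √[(20 - 12.57)² + (18.75 - 10)²] = -1.5.

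**2. Identical counts, 10/10/10 of 100.** p = 1.00, and the upper limit is √[(18.75 - 10)² + (10 - 5.08)²] = +10.0 points.

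**3. The same check at other assumed sizes.** The first table in each row is the largest Group I count that is still non-significant.

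| n per group | Counts | p | I minus III, 97.5% CI (points) | Upper limit if 10% in every group |
|---|---|---|---|---|
| 50 | 12/5/5 | 0.074 | +14 (-3.2 to +30.7) | +14.8 |
| 100 | 20/10/10 | 0.056 | +10 (-1.5 to +21.4) | +10.0 |
| 150 | 27/15/15 | 0.055 | +8 (-1.1 to +17.1) | +8.1 |

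Lower rates give smaller limits: 5/5/5 of 100 leaves +8.0 points, and 2/2/2 of 150 leaves +4.3.

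**4. A significant test.** With equal group sizes, chi-squared does not depend on which group holds which count. At 100 per group, 21/10/10 and 10/10/21 both give p = 0.033, although the first points against same-day discharge and the second against routine care. The frequency table shows the direction, but the p-value does not test either contrast with control.

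**5. The two analyses can disagree the other way.** One more Group I event makes each three-group test significant, while the 97.5% interval for I minus III still includes zero:
- 13/5/5 of 50: p = 0.037, CI -1.5 to +32.8.
- 21/10/10 of 100: p = 0.033, CI -0.6 to +22.5.
- 28/15/15 of 150: p = 0.035, CI -0.5 to +17.8.

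**6. Counting window.** Suppose the true complication rate from surgery is 10% in every group, and that 20% to 50% of events (assumed) fall between same-day and day-2 discharge. Post-discharge counting alone then shows an apparent excess in Group I of 10% × 0.2 = 2 points to 10% × 0.5 = 5 points.

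**The case against.** The strongest reply is that the documents promise an evaluation of safety and nothing more. They state no non-inferiority aim and no margin, and they nowhere say that non-significance will be read as safe. This stands. A reader might infer that the plan treats a non-significant test as proof of safety, but the text does not support that. The gap is in what will be estimated and reported.

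Next, the missing limit is recoverable. Frequency tables give counts and denominators, and anyone can compute a difference and interval from them, as was done here. This also stands, and it is why the point is an improvement and not a fatal flaw. It does not repair the window: tables of post-discharge events cannot restore in-hospital events that were not counted.

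A reader might also infer that the three-group test should give way to two Bonferroni contrasts. The reversals in step 5 argue against that, since the stricter contrast can include zero where the planned test flags a difference. With three groups, pairwise 5% tests made only after a significant three-group test also control the family-wise error. The 97.5% level is thus one reasonable choice for simultaneous intervals, and the documents do not force it. Nor do they name a primary outcome, so they give no basis for making complications the main analysis of the whole trial.

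Finally, the numbers rest on assumed sizes and rates, and the window effect on an assumed share of events. That is correct. The terms fail and clinical security are not defined in these documents and might already capture some in-hospital events. The omission itself depends on none of these numbers.

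**Conclusion.** The point holds as a cheap improvement. The SAP tests the four rates across three groups and tabulates them, but it gives no estimate with precision of Group I or Group II against the named control. Non-significance then leaves the excess risk unbounded, and significance does not formally locate the difference. The post-discharge endpoint starts on the day of surgery in Group I and on day 2 in Group III, with no common window, so it favours later discharge by design.

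The size is illustrative only. In the examples worked above (10% control rate, 50 to 150 per group), a non-significant result went with upper limits from about 8 to 31 points. That should not be read as a general range: at lower rates the limit is smaller, for example +4.3 points. The 2 to 5 point window effect likewise depends on the assumed timing of events.

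**What to change.** - Keep the planned three-group chi-squared or Fisher test, with its standing unchanged.
- For each of the four rates, add the risk difference for Group I vs III and for Group II vs III with a confidence interval (for example Newcombe). State in advance how the two contrasts are handled for multiplicity, for example by 97.5% intervals. That level covers the pair within one rate, not the four rates together.
- Add a complication rate counted from surgery over the same window in every group, whether the event occurs in hospital or after discharge, for example to the day-10 visit already planned. Base the between-group safety comparison of complications on it, and keep post-discharge complications as a secondary description.
- State in the SAP that a non-significant test alone will not be reported as evidence of safety.

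The cost is mostly wording and a little more analysis. In-hospital complications must be dated and recorded in all groups; the documents do not say whether this is already done. Intervals may be wide. A 97.5% contrast will sometimes include zero when the three-group test is significant, so both results should be reported together. The gain is a limit on excess risk and a direct comparison with control; it is not a gain in power.
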